#### Section C-1.2 Incidence rate of new depression or worsening of existing depression

Table C-1.2.1 Incidence rate of new depression or worsening of existing depression, ITT population, Complete cohort

	DNG		OAED			NAED		Allocation unknown	Total
		GnRH-a	Danazol	All OAED	CC	Other progestin	All NAED		
Number of women years	xx	xx	xx	xx	xx	xx	xx	xx	xx
Confirmed depression	xx	xx	xx	xx	xx	xx	xx	xx	xx
IR* (95% CI)	xx.x (xx.x-x.x)	xx.x (xx.x-x.x)	xx.x (xx.x-x.x)	xx.x (xx.x-x.x)					
Thereof									
Treated by psychiatrist	xx.x (xx.x-x.x)	xx.x (xx.x-x.x)	xx.x (xx.x-x.x)	xx.x (xx.x-x.x)	xx.x (xx.x–x.x)	xx.x (xx.x-x.x)	xx.x (xx.x-x.x)	xx.x (xx.x-x.x)	xx.x (xx.x–x.x)
	xx	xx	xx	xx	xx	XX	xx	xx	xx
Hospital admission	xx.x (xx.x-x.x)	xx.x (xx.x-x.x)	xx.x (xx.x-x.x)	xx.x (xx.x-x.x)	xx.x (xx.x–x.x)	xx.x (xx.x-x.x)	xx.x (xx.x–x.x)	xx.x (xx.x–x.x)	xx.x (xx.x–x.x)
	xx	xx	xx	xx	xx	xx	xx	xx	xx
Suicide attempt	xx.x (xx.x-x.x)	xx.x (xx.x-x.x)	xx.x (xx.x-x.x)	xx.x (xx.x-x.x)	xx.x (xx.x–x.x)	xx.x (xx.x-x.x)	xx.x (xx.x–x.x)	xx.x (xx.x–x.x)	xx.x (xx.x–x.x)
	xx	xx	xx	xx	xx	xx	xx	xx	xx
Committed suicide	xx.x (xx.x-x.x)	xx.x (xx.x-x.x)	xx.x (xx.x-x.x)	xx.x (xx.x-x.x)	xx.x (xx.x–x.x)	xx.x (xx.x-x.x)	xx.x (xx.x–x.x)	xx.x (xx.x–x.x)	xx.x (xx.x–x.x)
Personal history of	xx	XX	xx	xx	xx	XX	xx	xx	xx
depression	xx.x (xx.x-x.x)	xx.x (xx.x-x.x)	xx.x (xx.x-x.x)	xx.x (xx.x-x.x)	xx.x (xx.x–x.x)	xx.x (xx.x-x.x)	xx.x (xx.x–x.x)	xx.x (xx.x–x.x)	xx.x (xx.x–x.x)
Family history of	xx	xx	xx	xx	xx	xx	xx	xx	xx
depression	xx.x (xx.x-x.x)	xx.x (xx.x-x.x)	xx.x (xx.x-x.x)	xx.x (xx.x-x.x)					

Note: \* Incidence rate is shown per 10^4 women years.

Table C-1.2.2	Incidence rate of new depression or worsening of existing depression, AT population, Complete cohort
Table C-1.2.3	Incidence rate of new depression or worsening of existing depression, AT population, Starter
Table C-1.2.4	Incidence rate of new depression or worsening of existing depression, AT population, Switcher
Table C-1.2.5	Incidence rate of new depression or worsening of existing depression, AT population, Restarter
Table C-1.2.6	Incidence rate of new depression or worsening of existing depression, AT population, Diagnosis confirmed by surgery
Table C-1.2.7	Incidence rate of new depression or worsening of existing depression, AT population, Diagnosis based on clinical symptoms
Table C-1.2.8	Incidence rate of new depression or worsening of existing depression, AT population, Germany
Table C-1.2.9	Incidence rate of new depression or worsening of existing depression, AT population, Poland
Table C-1.2.10	Incidence rate of new depression or worsening of existing depression, AT population, Hungary
Table C-1.2.11	Incidence rate of new depression or worsening of existing depression, AT population, Switzerland
Table C-1.2.12	Incidence rate of new depression or worsening of existing depression, AT population, Russia
Table C-1.2.13	Incidence rate of new depression or worsening of existing depression, AT population, Ukraine

Supporting document SOP BMT 01.09 - Doc 5002.02 - Effective date 21.03.2017

#### Section C-1.3 Incidence proportions of treatment discontinuation due to treatment failure

Table C-1.3.1 Incidence proportions of treatment discontinuation due to treatment failure, AT population, Complete cohort

	DNG		OAED			NAED		Allocation unknown	Total
		GnRH-a	Danazol	All OAED	СНС	Other progestin	All NAED		
Number of treatment starts	xx	xx	xx	xx	xx	xx	xx	xx	xx
Treatment failure	xx	xx	xx	xx	xx	xx	xx	xx	xx
IP* (95% CI) Thereof**	xx.x (xx.x–x.x)	xx.x (xx.x–x.x)	xx.x (xx.x-x.x)	xx.x (xx.x-x.x)	xx.x (xx.x–x.x)	xx.x (xx.x-x.x)	xx.x (xx.x–x.x)	xx.x (xx.x–x.x)	xx.x (xx.x–x.x)
Medication ineffective	xx xx.x (xx.x–x.x)			xx xx.x (xx.x–x.x)	xx xx.x (xx.x-x.x)		xx xx.x (xx.x–x.x)		
Side effects  Thereof***	xx xx.x (xx.x-x.x)				xx xx.x (xx.x–x.x)			xx xx.x (xx.x-x.x)	
Depression / Depressive mood	xx xx.x (xx.x-x.x)			xx xx.x (xx.x–x.x)	xx xx.x (xx.x–x.x)			xx xx.x (xx.x–x.x)	
<category>></category>	xx xx.x (xx.x–x.x)			xx xx.x (xx.x-x.x)	xx xx.x (xx.x–x.x)			xx xx.x (xx.x–x.x)	

Note: \* Incidence proportion is shown per 10^2 treatment starts, including incident exposure at study entry, switches between exposure groups and/or restarts within exposure groups.

Note: \*\* Multiple answers possible.

Note: "Multiple answers possible. Only side effect categories with a proportion > 1% were displayed

Table C-1.3.2	Incidence proportions of treatment discontinuation due to treatment failure, AT population, Starter
Table C-1.3.3	Incidence proportions of treatment discontinuation due to treatment failure, AT population, Switcher
Table C-1.3.4	Incidence proportions of treatment discontinuation due to treatment failure, AT population, Restarter
Table C-1.3.5	Incidence proportions of treatment discontinuation due to treatment failure, AT population, Diagnosis confirmed by surgery
Table C-1.3.6	Incidence proportions of treatment discontinuation due to treatment failure, AT population, Diagnosis based on clinical symptoms
Table C-1.3.7	Incidence proportions of treatment discontinuation due to treatment failure, AT population, Germany
Table C-1.3.8	Incidence proportions of treatment discontinuation due to treatment failure, AT population, Poland
Table C-1.3.9	Incidence proportions of treatment discontinuation due to treatment failure, AT population, Hungary
Table C-1.3.10	Incidence proportions of treatment discontinuation due to treatment failure, AT population, Switzerland
Table C-1.3.11	Incidence proportions of treatment discontinuation due to treatment failure, AT population, Russia
Table C-1.3.12	Incidence proportions of treatment discontinuation due to treatment failure, AT population, Ukraine

Supporting document SOP BMT 01.09 - Doc 5002.02 - Effective date 21.03.2017

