1. INTRODUCTION

Endometriosis is a common, chronic, gynecological disease characterized by pain and impaired fertility. Prevalence estimates vary widely, however, the proportion of premenopausal women living with endometriosis is thought to be approximately 10% [1]. Endometriosis causes chronic inflammation, ovarian cyst formation, fibrosis and adhesions [1]. There seems to be little correlation between the extent of the disease and severity of pain experienced [2]. However, symptoms seem to respond to decreased circulating estrogen [3] and the mainstay of medical treatment is hormonal induced anovulation and a reduction in endogenous estrogen production.

While currently approved medications for endometriosis have proven to be effective in decreasing pelvic pain, many have clinically relevant side-effects. Danazol, a testosterone analogue, can cause androgenization and GnRH agonists are known to decrease bone mineral density. Consequently, treatment for endometriosis with these medications needs to be stopped after 6-12 months. Post-treatment endometrial lesions tend to regenerate, with many women's symptoms reoccurring 1-2 months after the cessation of treatment. Some countries in Europe also allow the use of progestogens for the treatment of endometriosis, however, there is currently no pharmaceutical preparation licensed for the treatment of endometriosis in all member states of the European Union.³

Dienogest (DNG) is a 19-nortestosterone derivative progestogen that is highly selective for progesterone receptors [4]. DNG has been available as part of a low-dose combined oral contraceptive containing 2mg of dienogest and 30µg of ethinylestradiol (DNG/EE) in Germany since 1995. As a progestin in DNG/EE, DNG is known for having strong endometrial effects that improve dysmenorrhoea and decrease the duration of menstrual bleeding [5]. In addition, progestogens may also modulate pain associated with endometriosis by dampening neuronal activity [3]. As a monotherapy for the treatment of endometriosis DNG 2mg/day has been available in Japan since 2008. In Japan it has been found to be a reliable and effective treatment for dysmenorrhea, premenstrual pain, dyspareunia and diffuse pelvic pain associated with endometriosis associated pelvic pain with improved tolerability compared with 3.75mg leuprolide acetate (LA) [7-8]. Unlike LA, DNG has minimal effects on bone density and may offer women a new option for the long-term control of endometriosis symptoms.

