There are both pharmacological and clinical indications that suggest that DNG may be superior to other endometriosis medications as a long-term treatment for endometriosis. That is, a statistical comparison of DNG vs. other endometriosis medications may show a difference in 'treatment failure', with DNG users continuing on treatment for longer periods of time. 'Treatment failure' is defined as cessation of treatment caused by lack of efficacy, loss of efficacy or an adverse drug reaction and does not include women who stop treatment after pre-defined treatment periods (e.g. after six months for GnRH agonists). In addition, combined treatment with GnRH, an estrogen and/or a progestogen (add-back therapy) will be considered as a single treatment regimen. In cases where add-back therapy is used the predefined end-point is the cessation of the add-back therapy. A superiority design to investigate 'treatment failure' for DNG has been chosen. The analysis will be based on a 5%-point difference (difference of 0.05) of DNG vs. other endometriosis medications.  $OR_{TreatmentFailure}$  is defined as the odds ratio for 'treatment failure' for DNG vs. OAED.

 $H_0: OR_{TreatmentFailure} \ge 1$ 

 $H_A: OR_{Treatmentfailure} < 1$ 

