#### 5.4.1 Incidence measures

The *incidence rate* (IR) measures the occurrence of new cases per unit of person-time.

$$IR = \frac{Number\ of\ new\ cases}{Total\ follow - up\ time}$$

The incidence rate takes into consideration the patient-specific follow-up time and it assumes a constant hazard rate. For each of n subjects the time  $t_k (k=1,...,K)$  to: (1) the end of the risk period, if recurrent events are allowed or (2) to the first occurrence of a certain event is observed. If the event was not experienced, the (censored) time to the end of the risk period is observed.

In the present study, women-years are conducted as a unit of person-time. Incidence rates are shown per 10^4 women-years (WY) unless otherwise specified.

The *incidence rate ratio* (IRR) is the proportion of two incidence rate estimates.

$$IRR = \frac{Incidence\ rate\ of\ treatment\ group}{Incidence\ rate\ of\ control\ group}$$

Supporting document SOP BMT 01.09 – Doc 5002.02 – Effective date 21.03.2017

The incidence rate ratio gives a measure of how much more likely an event occurs in subjects under exposure (treatment group) than in subjects who were not exposed (control group).

The *incidence proportion* (IP) measures the occurrence of new cases in relation to the size of the population at risk within a given period of time (cumulative incidence).

$$IP = \frac{Number\ of\ new\ cases}{Size\ of\ population\ at\ risk}$$

Exact 95% confidence intervals for prevalence, incidence proportion, incidence rate, and incidence rate ratio will be calculated in accordance with Clopper and Pearson[9].

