#### Section B-7 Distribution and selected baseline characteristics of Visanne long-term user

#### Section B-7.1 Duration of Visanne use

Table B-7.1.1 Duration of Visanne use

	DNG long-term user*
Number (%) of women	xx ( 100%)
Duration of DNG use	
15 months to < 24 months	xx ( xx.x%)
24 months to < 30 months	xx ( xx.x%)
30 months to < 36 months	xx ( xx.x%)
36 months to < 42 months	xx ( xx.x%)
42 months to < 48 months	xx ( xx.x%)
48 months to < 54 months	xx ( xx.x%)
54 months to < 60 months	xx ( xx.x%)
60 months to < 66 months	xx ( xx.x%)
66 months to < 72 months	xx ( xx.x%)
72 months to < 78 months	xx ( xx.x%)
78 months to < 84 months	xx ( xx.x%)
84 months and more	xx ( xx.x%)

Note: \*Long-term: defined as continuous use for >= 15 months. They may have started with other than DNG treatment.

Table B-7.1.2	Duration of Visanne use, Starter
Table B-7.1.3	Duration of Visanne use, Switcher
Table B-7.1.4	Duration of Visanne use, Restarter
Table B-7.1.5	Duration of Visanne use, Diagnosis confirmed by surgery
Table B-7.1.6	Duration of Visanne use, Diagnosis based on clinical symptoms
Table B-7.1.7	Duration of Visanne use, Germany
Table B-7.1.8	Duration of Visanne use, Poland
Table B-7.1.9	Duration of Visanne use, Hungary
Table B-7.1.10	Duration of Visanne use, Switzerland
Table B-7.1.11	Duration of Visanne use, Russia
Table B-7.1.12	Duration of Visanne use. Ukraine

Supporting document SOP BMT 01.09 – Doc 5002.02 – Effective date 21.03.2017

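### Treatment failure per treatment start has no time window, so time-limited comparator courses and open-ended DNG use are not compared over equal time

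*SAP*

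**What the plan says.** - **The proportion.** SAP mock Table C-1.3.1 divides treatment failures by treatment starts, "including incident exposure at study entry, switches between exposure groups and/or restarts within exposure groups". Table C-2.4.1 does the same for adolescents. Neither sets a time horizon.
- **The SAP's own definition.** SAP 5.4.1 says an incidence proportion counts new cases "in relation to the size of the population at risk within a given period of time". No period is given for treatment failure.
- **Comparator courses.** OAED consists of GnRH agonists and danazol (SAP 3.2 and 5.1). Protocol section 1 says of these drugs that "treatment for endometriosis with these medications needs to be stopped after 6-12 months". SAP 5.2 adds that treatment failure "does not include women who stop treatment after pre-defined treatment periods (e.g. after six months for GnRH agonists"). There is an exception: "In cases where add-back therapy is used the predefined end-point is the cessation of the add-back therapy".
- **DNG courses.** No maximum is stated. SAP 5.2 anticipates a difference "with DNG users continuing on treatment for longer periods of time", and the duration categories in Table B-7.1.1 run to "84 months and more". SAP section 3 sets follow-up at 2 to 7 years.
- **The hypothesis.** SAP 5.2 frames superiority as a 5-point difference and as an odds ratio below 1. SAP 5.4.2 specifies only a Cox model. Section D-3 plans an incidence rate ratio (IRR) and crude and adjusted Cox hazard ratios (HRs) for treatment failure.

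**The concern.** A failure can be recorded only while a woman is on the drug. An OAED course that ends as planned stays in the denominator and can no longer fail, whereas a DNG start remains able to fail for as long as it continues. The per-start proportion therefore mixes the risk of failure with the length of time for which the drug is used. Repeat GnRH courses after a break of at least 4 weeks add further OAED starts, while continuous DNG use counts once.

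Treatment failure is one of three primary outcomes, and SAP 5.2 words its hypothesis on proportion scales. No odds-ratio model is specified and D-3 contains no proportions. Anyone following 5.2 literally would turn to C-1.3.1, where part of the contrast comes from planned course length.

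**Working it through.** **Plan's own figure.** Table 4 gives 2,950 DNG and 1,475 reference women-years for 0.25 vs 0.30, 90% power and one-sided alpha 0.0167. Treating women-years as independent binary units at 2:1, the two-proportion formula gives 2,764 and 1,382. The stated size has 91.8% power; 2,950 and 1,475 come out exactly at one-sided 0.0125. This mismatch is a separate matter and does not bear on the point here.

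**Inputs.** Failure hazard h = 0.30 per woman-year (WY), reading the SAP section 4 figure of at least 0.3 as a rate. OAED course T = 0.5 or 1 year (protocol section 1). Two inputs are assumptions because the documents do not give them: maximum time on DNG (2 or 3 years; planned observation averages 89,086/25,002 = 3.6 WY per woman) and other stopping o (0 to 1.0 per WY).

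**Formula.** Proportion of starts that fail by time T: F(T) = h/(h+o) × (1 − exp(−(h+o)T)).

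Example with h = o = 0.30: F(0.5) = 0.5 × (1 − e^−0.3) = 13.0%; F(1) = 0.5 × (1 − e^−0.6) = 22.6%; F(3) = 0.5 × (1 − e^−1.8) = 41.7%.

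**Equal hazard of 0.30 in both cohorts** (proportions in %; gap = DNG minus OAED, in points, for the 12-month and the 6-month course):

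| o per WY | OAED 6 mo | OAED 12 mo | DNG 2 y | DNG 3 y | Gap at 2 y | Gap at 3 y |
|---|---|---|---|---|---|---|
| 0 | 13.9 | 25.9 | 45.1 | 59.3 | 19-31 | 33-45 |
| 0.3 | 13.0 | 22.6 | 34.9 | 41.7 | 12-22 | 19-29 |
| 0.5 | 12.4 | 20.7 | 29.9 | 34.1 | 9-18 | 13-22 |
| 1.0 | 11.0 | 16.8 | 21.4 | 22.6 | 5-10 | 6-12 |

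If failure is front-loaded (0.5 per WY for 6 months, then 0.1) with o = 0.3, the 3-year gap is 8-11 points. With no other stopping, the gap reaches 5 points once DNG courses last 0.70 years (6-month comparator course) or 1.23 years (12-month course).

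**A true DNG benefit.** Take 0.25 for DNG and 0.30 for OAED. With o = 0.3, DNG shows 36.7% at 3 years against 13.0% or 22.6%. With o = 1.0, it shows 19.5% against 11.0% or 16.8%. The sign is wrong in each case. Cut at a common 6 months with o = 0.3, the figures are 10.9% vs 13.0%, in the right direction.

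**Is a 12-month window enough?** Not if planned completion is a competing event and courses last 6 months. Equal hazards then give OAED 13.0% and DNG 22.6% (o = 0.3), or 13.9% and 25.9% (o = 0).

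**Power of a 6-month proportion.** With hazards 0.25 and 0.30 and no other stopping, 6 months gives 11.8% vs 13.9%, a difference of 2.2 points. At 2,950 and 1,475 units and one-sided 0.0167, power is about 48%.

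**The case against.** The best reply is that C-1.3.1 is a per-cohort description with no test, and that comparison belongs to Section D. D-3 plans an IRR and Cox HRs, which use person-time; with equal constant hazards both have an expected value of about 1 whatever the course length. This stands, and it limits the point to the proportion and to statements in the form that SAP 5.2 uses.

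Other tables also expose the mechanism. C-2.1.1 shows planned completions by drug. B-8.12.1 times the first switch within 6 months, at 7-12 months and later. B-9.3.1 counts failures at the first stop or switch from the baseline prescription. None of these is a failure proportion over a common window.

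The cap is soft: it is introductory background in a non-interventional study, add-back can extend a regimen, it does not cover the non-approved cohort, and C-3.4.1 has GnRH-a and danazol columns for at least 15 months of continuous use. Hence courses are generally, not always, time-limited. Restarts count in every cohort, and nothing in the documents shows that repeat courses are made mainly by women who tolerated the last one.

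A reader might infer that the table must mislead by tens of points, or that DNG would look worse whatever the truth. The documents support neither. The size rests on assumed durations and stopping rates. With h = o = 0.30 for OAED and 4 years of possible DNG use, DNG shows the lower proportion once its hazard is below about 0.39 (12-month courses) or 0.20 (6-month courses) times the comparator's.

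**Conclusion.** The point holds for the per-start proportions in C-1.3 and C-2.4 and for any 5-point or odds-ratio statement taken from them. They depart from SAP 5.4.1 and give the cohorts unequal time in which to fail.

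At the plan's rate of 0.30 per WY in both cohorts, the spurious excess for DNG is roughly 5 to more than 30 points, which equals or exceeds the 5-point design difference. It can reverse the sign of a modest true benefit. This assumes OAED courses of 6-12 months, DNG use of up to 2-3 years and other stopping of 0 to 1.0 per WY. A failure hazard of 0.10 per WY, well below the plan's figure, with other stopping at 1.0 per WY would shrink the gap to about 2-5 points.

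It does not follow that the study cannot answer its treatment-failure question. The D-3 analyses can, provided the SAP says that they carry the test.

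**What to change.** 1. In SAP 5.2, state that the superiority test for treatment failure is the D-3 Cox HR, with planned completion and other non-failure stops censored. Drop the odds-ratio and 5-point wording or align it with that test.
2. In C-1.3 and C-2.4, report the cumulative incidence of failure by 6 months after starting the baseline prescription, with one episode per woman and non-failure stops as competing events. Base any proportion-type statement on that window.
3. If a 12-month figure is shown, censor at planned completion or label the figure as not comparable between cohorts.
4. Show later switches and restarts in a separate table.

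The cost is SAP and table-shell wording plus programming. The follow-up questionnaire already collects start and stop dates and reasons, including planned completion. There are two downsides. Failures after 6 months would enter only the HR, the IRR and descriptive tables. The 6-month proportion has low power (about 48% at the Table 4 size), so it should be descriptive or supportive.

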#### Section C-2 Secondary outcomes

Section C-2.1 Incidence proportions of treatment discontinuation unrelated to treatment failure

Table C-2.1.1 Incidence proportions of treatment discontinuation unrelated to treatment failure, AT population, Complete cohort

	DNG		OAED			NAED		Allocation unknown	Total
		GnRH-a	Danazol	All OAED	СНС	Other progestin	All NAED		
Number of treatment starts	xx	xx	xx	xx	xx	xx	xx	xx	xx
Treatment									
discontinuation	XX	XX	XX	XX	XX	xx	xx	xx	xx
IP* (95% CI)	xx.x (xx.x-x.x)	xx.x (xx.x-x.x)	xx.x (xx.x–x.x)	xx.x (xx.x-x.x)	xx.x (xx.x-x.x)	xx.x (xx.x-x.x)	xx.x (xx.x–x.x)	xx.x (xx.x–x.x)	xx.x (xx.x-x.x)
Thereof**									
Trying to become	XX	xx	xx	XX	xx	xx	XX	xx	xx
pregnant	xx.x (xx.x-x.x)	xx.x (xx.x-x.x)	xx.x (xx.x-x.x)	xx.x (xx.x-x.x)	xx.x (xx.x–x.x)	xx.x (xx.x-x.x)	xx.x (xx.x-x.x)	xx.x (xx.x-x.x)	xx.x (xx.x-x.x)
Treatment duration	xx	xx	xx	XX	xx	xx	XX	xx	xx
finished	xx.x (xx.x-x.x)	xx.x (xx.x-x.x)	xx.x (xx.x-x.x)	xx.x (xx.x-x.x)	xx.x (xx.x–x.x)	xx.x (xx.x-x.x)	xx.x (xx.x-x.x)	xx.x (xx.x-x.x)	xx.x (xx.x-x.x)
Other	xx	xx	xx	xx	xx	xx	xx	xx	xx
	xx.x (xx.x-x.x)	xx.x (xx.x-x.x)	xx.x (xx.x-x.x)	xx.x (xx.x-x.x)					
Thereof**									
Physician's advice	xx	xx	xx	xx	XX	xx	xx	xx	xx
	xx.x (xx.x-x.x)	xx.x (xx.x-x.x)	xx.x (xx.x-x.x)	xx.x (xx.x-x.x)					
< <category>></category>	xx	xx	xx	xx	XX	xx	xx	xx	xx
	xx.x (xx.x–x.x)	xx.x (xx.x-x.x)	xx.x (xx.x-x.x)	xx.x (xx.x-x.x)	xx.x (xx.x–x.x)	xx.x (xx.x-x.x)	xx.x (xx.x-x.x)	xx.x (xx.x-x.x)	xx.x (xx.x-x.x)

Note: 'Incidence proportion is shown per 102 treatment starts, including incident exposure at study entry, switches between exposure groups and/or restarts within exposure groups.

Note: \*\*Multiple answers possible.

Table C-2.1.2	Incidence proportions of treatment discontinuation unrelated to treatment failure, AT population, Starter
Table C-2.1.3	Incidence proportions of treatment discontinuation unrelated to treatment failure, AT population, Switcher
Table C-2.1.4	Incidence proportions of treatment discontinuation unrelated to treatment failure, AT population, Restarter
Table C-2.1.5	Incidence proportions of treatment discontinuation unrelated to treatment failure, AT population, Diagnosis confirmed by surgery
Table C-2.1.6	Incidence proportions of treatment discontinuation unrelated to treatment failure, AT population, Diagnosis based on clinical symptoms
Table C-2.1.7	Incidence proportions of treatment discontinuation unrelated to treatment failure, AT population, Germany
Table C-2.1.8	Incidence proportions of treatment discontinuation unrelated to treatment failure, AT population, Poland
Table C-2.1.9	Incidence proportions of treatment discontinuation unrelated to treatment failure, AT population, Hungary
Table C-2.1.10	Incidence proportions of treatment discontinuation unrelated to treatment failure, AT population, Switzerland
Table C-2.1.11	Incidence proportions of treatment discontinuation unrelated to treatment failure, AT population, Russia
Table C-2.1.12	Incidence proportions of treatment discontinuation unrelated to treatment failure, AT population, Ukraine

Supporting document SOP BMT 01.09 – Doc 5002.02 – Effective date 21.03.2017

